# **B.** Tables for Laboratory Abnormalities

The laboratory values provided in the tables below serve as guidelines and are dependent upon institutional normal parameters. Institutional normal reference ranges should be provided to demonstrate that they are appropriate.

Serum*	Mild (Grade 1)	Moderate (Grade 2)	Severe (Grade 3)	Potentially Life Threatening (Grade 4)**
Sodium – Hyponatremia mEq/L	132 – 134	130 - 131	125 – 129	< 125
Sodium – Hypernatremia mEq/L	144 – 145	146 – 147	148 - 150	> 150

Serum*	Mild (Grade 1)	Moderate (Grade 2)	Severe (Grade 3)	Potentially Life Threatening (Grade 4)**
Potassium – Hyperkalemia mEq/L	5.1 - 5.2	5.3 - 5.4	5.5 - 5.6	> 5.6
Potassium – Hypokalemia mEq/L	3.5 - 3.6	3.3 – 3.4	3.1 – 3.2	< 3.1
Glucose – Hypoglycemia mg/dL	65 - 69	55 - 64	45 - 54	<45
Glucose – Hyperglycemia Fasting – mg/dL Random – mg/dL	$     \begin{array}{r}       100 - 110 \\       110 - 125     \end{array} $	111 – 125 126 – 200	>125 >200	Insulin requirements or hyperosmolar coma
Blood Urea Nitrogen BUN mg/dL	23 - 26	27 - 31	> 31	Requires dialysis
Creatinine – mg/dL	1.5 – 1.7	1.8 - 2.0	2.1 – 2.5	> 2.5 or requires dialysis
Calcium – hypocalcemia mg/dL	8.0 - 8.4	7.5 – 7.9	7.0 - 7.4	< 7.0
Calcium – hypercalcemia mg/dL	10.5 - 11.0	11.1 – 11.5	11.6 - 12.0	> 12.0
Magnesium – hypomagnesemia mg/dL	1.3 – 1.5	1.1 – 1.2	0.9 - 1.0	< 0.9
Phosphorous – hypophosphatemia mg/dL	2.3 – 2.5	2.0 - 2.2	1.6 – 1.9	< 1.6
CPK – mg/dL	1.25 – 1.5 x ULN***	1.6 – 3.0 x ULN	3.1 –10 x ULN	>10 x ULN
Albumin – Hypoalbuminemia g/dL	2.8 - 3.1	2.5 – 2.7	< 2.5	
Total Protein – Hypoproteinemia g/dL	5.5 - 6.0	5.0 - 5.4	< 5.0	
Alkaline phosphate – increase by factor	1.1 – 2.0 x ULN	2.1 – 3.0 x ULN	3.1 – 10 x ULN	>10 x ULN
Liver Function Tests – ALT, AST increase by factor	1.1 – 2.5 x ULN	2.6 – 5.0 x ULN	5.1 – 10 x ULN	> 10 x ULN
Bilirubin – when accompanied by any increase in Liver Function Test increase by factor	1.1 – 1.25 x ULN	1.26 – 1.5 x ULN	1.51 – 1.75 x ULN	> 1.75 x ULN
Bilirubin – when Liver Function Test is normal; increase by factor	1.1 – 1.5 x ULN	1.6 – 2.0 x ULN	2.0 – 3.0 x ULN	> 3.0 x ULN
Cholesterol	201-210	211 - 225	> 226	
Pancreatic enzymes – amylase, lipase	1.1 – 1.5 x ULN	1.6 – 2.0 x ULN	2.1 – 5.0 x ULN	> 5.0 x ULN

\* The laboratory values provided in the tables serve as guidelines and are dependent upon institutional normal parameters. Institutional normal reference ranges should be provided to demonstrate that they are appropriate. \*\* The clinical signs or symptoms associated with laboratory abnormalities might result in characterization of the laboratory abnormalities as Potentially Life Threatening (Grade 4). For example, a low sodium value that falls within a grade 3 parameter (125-129 mE/L) should be recorded as a grade 4 hyponatremia event if the subject had a new seizure associated with the low sodium value.

\*\*\* "ULN" is the upper limit of the normal range.

Hematology*	Mild (Grade 1)	Moderate (Grade 2)	Severe (Grade 3)	Potentially Life Threatening (Grade 4)
Hemoglobin (Female) - gm/dL	11.0 - 12.0	9.5 - 10.9	8.0 - 9.4	< 8.0
Hemoglobin (Female) decrease from baseline value - gm/dL	not applicable	1.6 – 2.0	2.1 – 5.0	> 5.0
Hemoglobin (Male) - gm/dL	12.5 – 13.5	10.5 - 12.4	8.5 - 10.4	< 8.5
Hemoglobin (Male) decrease from baseline value – gm/dL	not applicable	1.6 – 2.0	2.1 – 5.0	> 5.0
WBC Increase - cell/mm 	10,800 - 15,000	15,001 - 20,000	20,001 - 25,000	> 25,000
WBC Decrease - cell/mm 	2,500 - 3,500	1,500 - 2,499	1,000 - 1,499	< 1,000
Lymphocytes Decrease - cell/mm 	750 – 1,000	500 - 749	250 - 499	< 250
Neutrophils Decrease - cell/mm 	1,500 - 2,000	1,000 - 1,499	500 - 999	< 500
Eosinophils - cell/mm 	650 - 1500	1501 - 5000	> 5000	Hypereosinophilic
Platelets Decreased - cell/mm 	125,000 - 140,000	100,000 - 124,000	25,000 - 99,000	< 25,000
PT – increase by factor (prothrombin time)	1.10 x ULN**	1.11 – 1.20 x ULN	1.21 – 1.25 x ULN	>1.25 ULN
PTT – increase by factor (partial thromboplastin time)	1.10 – 1.20 x ULN	1.21 – 1.4 x ULN	1.41 – 1.5 x ULN	> 1.5 x ULN
Fibrinogen increase - mg/dL	400 - 500	501 - 600	> 600	
Fibrinogen decrease - mg/dL	150 - 200	125 – 149	100 - 124	< 100 or associated with gross bleeding or disseminated intravascular coagulation (DIC)

\* The laboratory values provided in the tables serve as guidelines and are dependent upon institutional normal parameters. Institutional normal reference ranges should be provided to demonstrate that they are appropriate.

### LIST OF ABBREVIATIONS

Abbreviation	Term
PDL	primary diagnostic laboratory
PI	Principal Investigator
PP	per protocol
PSRT	Protocol Safety Review Team
PT	preferred term
RNA	ribonucleic acid
RVP	reporter virus particle
SAE	serious adverse event
SAP	statistical analysis plan
SOC	System organ class
TBD	to be determined
TFL	tables, figures, and listings
US	United States
VE	vaccine efficacy
VRC	Vaccine Research Center
WBC	white blood cell
WHO	World Health Organization
WNV	West Nile virus
ZIKV	Zika virus
ZIKVwt	Zika virus wild-type

# List of Abbreviations (continued)

#### 1. **PREFACE**

The Statistical Analysis Plan (SAP) for "A Phase 2/2B, Randomized Trial to Evaluate the Safety, Immunogenicity and Efficacy of a Zika virus DNA Vaccine in Healthy Adults and Adolescents" (VRC 705) describes and expands upon the statistical information presented in the protocol.

This document describes all planned analyses that will be conducted by the VRC 705 Data Center and provides reasons and justifications for these analyses. It also includes sample tables, figures, and listings (TFL) planned for the final analyses. Regarding the final analyses, this SAP follows the International Conference on Harmonisation of Technical Requirements for Registration of Pharmaceuticals for Human Use (ICH) Guidelines, as indicated in Topic E3 (Structure and Content of Clinical Study Reports), and more generally is consistent with Topic E8 (General Considerations for Clinical Trials) and Topic E9 (Statistical Principles for Clinical Trials). The structure and content of the SAP provides sufficient detail to meet the requirements identified by the Food and Drug Administration (FDA) and ICH, while all work planned and reported for this SAP will follow internationally accepted guidelines published by the American Statistical Association and the Royal Statistical Society for statistical practice.

This document contains four sections: (1) a review of the study design, (2) general statistical considerations, (3) comprehensive statistical analysis methods for efficacy and safety endpoints, and (4) a list of proposed TFLs (Appendices 1, 2, and 3).

Following any protocol amendment, this SAP will be reviewed and revised to address any changes in the protocol impacting analysis. Any deviation from the final SAP will be described and justified. The reader of this SAP is encouraged to also review the study protocol for details on conduct of the study and the operational aspects of clinical assessments.

# 2. INTRODUCTION

The Dale and Betty Bumpers Vaccine Research Center (VRC), National Institute of Allergy and Infectious Diseases (NIAID), National Institutes of Health (NIH) (Bethesda, MD, USA) is dedicated to translating the latest knowledge of disease pathogenesis and immunology into new vaccine strategies to provide safe and effective means to prevent and control infectious diseases. Zika virus (ZIKV) is a mosquito-borne infection causing illness with mild symptoms including fever, rash, joint paint and conjunctivitis that may last for several days to weeks.

Since its discovery in Uganda in 1947, outbreaks of ZIKV have been reported in Africa, Southeast Asia, and the Pacific Islands. ZIKV emerged in Brazil in 2015 and then rapidly spread throughout the Americas [1]. In May 2015, the Pan American Health Organization (PAHO) issued an alert regarding the first confirmed ZIKV infection in Brazil and on February 1, 2016, the World Health Organization (WHO) declared ZIKV a public health emergency of international concern due to evidence suggesting ZIKV infection may be linked to recent clusters of microcephaly in babies born to infected mothers and other reported neurological disorders including Guillain-Barré syndrome (GBS) [2]. According to the WHO, local transmission has now been reported in many other countries and territories and will continue to spread to new areas.

There are currently no effective vaccines or therapies against ZIKV. The rapid emergence of ZIKV supports the need for a safe and immunogenic vaccine. This protocol is designed as a Phase 2B evaluation of the investigational ZIKV DNA vaccine, VRC-ZKADNA090-00-VP. This candidate vaccine was evaluated in a Phase 1 study (VRC 320, NCT02996461).

VRC 705 is a multicenter, randomized, clinical trial evaluating the safety, immunogenicity, and efficacy of a three-dose vaccination regimen with the Zika virus (ZIKV) wild-type (ZIKVwt) DNA vaccine, VRC-ZKADNA090-00-VP. This Phase 2/2B study is being advanced rapidly to follow the initiation of the Phase 1 studies due to the significant public health need for a vaccine to prevent ZIKV. The study includes two Parts: **Part A** is an open-label evaluation of 90 subjects randomized to one of 3 groups to receive a 4 mg or 8mg dose of vaccine split between 2 or 4 injections; **Part B** is a double-blinded evaluation of 2400 subjects randomized to receive ZIKV vaccine or placebo.

## 2.1. Purpose of the Analyses

Note, not all analyses for endpoints included in the protocol are detailed in this plan. The exploratory endpoint analyses are not included in this SAP.

In **Part A**, the primary objective is to evaluate the safety and tolerability of the vaccine. In **Part B**, the primary objectives are to evaluate the safety and efficacy of the vaccine compared to the placebo. Secondary and exploratory objectives of the study relate to immunogenicity and durability of immune responses.

The VRC 705 protocol calls for multiple planned interim analyses. During **Part A** of the study immunogenicity may be analyzed in an ongoing fashion. During **Part B** of the study the following interim analyses will be performed:

- 1. Interim immunogenicity analyses may be performed after the neutralizing antibody (NAb) assays up to and including Week 12 have been completed on a subset of subjects.
- 2. Interim efficacy analysis may be performed when the total number of ZIKV cases in the modified Intent-to-treat (mITT) cohort reaches 30 and 60.

For **Part B**, the final efficacy analysis will occur when the total number of virologic ZIKV cases in the mITT cohort reaches 90 or study completion. The final analysis of **Part A** and **Part B** will be performed and completed when all primary and secondary safety, efficacy, and immunogenicity endpoint data are available, and the study database has been locked. The study clinical database and immunogenicity/efficacy database will be locked separately; the final analysis of **Part A** and **Part B** safety data will follow the clinical database lock and the final analysis of **Part A** and **Part B** immunogenicity and efficacy data will follow the second database lock once all lab data are received and validated.

#### **3. STUDY OBJECTIVES AND ENDPOINTS**

#### **3.1. Study Objectives**

Refer to Protocol Section 3, "Study Objectives."

#### 3.2. Endpoints

Refer to Protocol Section 6.2, "Endpoints."

#### 3.2.1. Study Definitions and Derived Variables

The baseline value will be defined as the last value obtained prior to the receipt of the first product administration on Day 0 (Visit 02).

Individual neutralization antibody (NAb) assay results will be reported as a titer. Fold-rise (NAb) is a measure that describes how much the NAb titer changes from an initial to a final value. The fold-rise is calculated as the ratio of the final value to the initial value. Subjects will be tested for baseline ZIKV serostatus based on serum samples collected at screening, Visit 01.

## 4. INVESTIGATIONAL PLAN

#### 4.1. Overall Study Design and Plan

Refer to Protocol Precis.

#### 4.2. Discussion of Design, Including the Choice of Control Group

Refer to Protocol Section 4, "Study Design and Clinical Procedures."

#### 4.3. Selection of Study Population

Refer to Protocol Precis.

#### 4.4. Study Product Administrations

#### 4.4.1. Study Product

Refer to Protocol Section 2, "Study Products".

#### 4.4.2. Vaccine Dose and Administration Method

Refer to Protocol Section 1.5, "Rationale for Study Product Dose and Administration Method."

#### 4.4.3. Method of Assigning Subjects to Study Groups (Randomization)

Refer to Protocol Section 6.4.6, "Randomization of Treatment Assignments and Unblinding Criteria."

#### 4.4.4. Blinding and Conditions for Unblinding

Refer to Protocol Section 6.4.6, "Randomization of Treatment Assignments and Unblinding Criteria."

Please refer to the Study Blinding Plan for additional details on blinding and processes for planned and unplanned unblinding events.

#### 5. SAMPLE SIZE CONSIDERATIONS

Refer to Protocol Section 6.3, "Sample Size and Accrual."

# 6. GENERAL STATISTICAL CONSIDERATIONS

#### 6.1. General Principles

Summary tables will be presented separately for **Part A** and **Part B**, and will mostly be structured with columns summarizing the groups as follows:

Part A

- Group 1: 4 mg ZIKVwt DNA, 2 injections
- Group 2: 4 mg ZIKVwt DNA, 4 injections
- Group 3: 8 mg ZIKVwt DNA, 4 injections
- All Part A Subjects.

Since the primary safety objective indicates assessing the 4mg dose regardless of the number of injections, safety data will be tabulated with the following columns.

- Group 1: 4 mg ZIKVwt DNA, 2 injections
- Group 2: 4 mg ZIKVwt DNA, 4 injections
- Groups 1 + 2: 4mg ZIKVwt DNA, 2 or 4 injections
- Group 3: 8 mg ZIKVwt DNA, 4 injections
- All Part A Subjects.

#### Part B

- Group 4: 4 mg ZIKVwt DNA
- Group 5: Placebo
- All Part B Subjects.

The total sample size for each summary group for the applicable analysis population being tabulated will be displayed in all tables.

All continuous variables will be summarized using the following descriptive statistics: n (nonmissing sample size), mean (or geometric mean, as appropriate), standard deviation, median, minimum and maximum. The frequency and percentages (denominators based on the non-missing sample size) of observed levels will be reported for all categorical measures. Unless otherwise specified, Clopper-Pearson exact methodology will be used to calculate CIs for proportions. All logarithmic transformations will be done using the natural log.

In presenting statistical inferences, the statistical claim (i.e. null and alternative hypotheses) will be clearly stated, the method used for hypothesis testing or CI estimation will be described and appropriately referenced, and the assumptions underlying the methods will be validated.

All data will be included in listings, sorted by study group and subject, and when appropriate by administration number and/or visit number within subject. Listings will be presented with **Part A** and **Part B** data separated.

### 6.2. Timing of Analyses

- 1. Interim immunogenicity analyses for **Part A** may be performed on an ongoing basis, per sponsor directive.
  - a) The first interim immunogenicity analysis will be performed when 10 subjects in each group have data available through Visit 05
- 2. Interim immunogenicity analyses for **Part B** may be performed on a subset of subjects after the NAb assays up to and including Week 12 have been completed for the subset of subjects.
- 3. Final Efficacy Analysis will occur when the total number of mITT virologic ZIKV cases (primary efficacy endpoint) in **Part B** of the study reaches 90 or study completion.
- 4. The Final Analysis of safety data for both Part A and Part B will be performed after clinical database lock when all subjects have been followed through 32 weeks after the last product administration for Part A and at least 6 months after the first product administration for Part B. Final analysis of the efficacy and immunogenicity endpoint data will follow the database lock of the immunogenicity and efficacy data once all lab data are received and validated.
- 5. Exploratory Immunogenicity Analyses may be completed following database lock as assay results become available.

For all analyses completed prior to database lock, individual subjects' study group assignments will not be unblinded with the possible exception of a review of selected AEs or episodes of ZIKV disease for safety monitoring requirements, as described in the Study Blinding Plan.

#### 6.3. Analysis Populations

The two parts of the study share the following definition for each type of analysis population:

All Enrolled Subjects: all subjects who enrolled in the screening segment. This population will be used for summaries of subject disposition, eligibility, demographics and the serious adverse event listing.

**Safety population**: all randomized subjects in the study who receive at least one study product administration, and have at least one post-administration safety assessment, analyzed according to the study product received. If it is unknown what study product was received, subjects will be summarized according to the randomized treatment assignment. This population will be used for analysis of all safety endpoints.

The **Intent-to-treat (ITT)** population will include all randomized subjects, analyzed according to the randomized study product. The ITT population will be used to analyze immunogenicity and efficacy analyses.

The **Modified intent-to-treat (mITT)** analyses will include all randomized subjects who remain event-free one week after all planned product administrations, where event is the primary efficacy event of a positive ZIKV PCR or other Zika test result with or without symptoms, analyzed according to the randomized study product. The mITT population will be used for immunogenicity and efficacy analyses (**Part B** only).

The **Per Protocol (PP)** analyses will include all subjects receiving three administrations within window as assigned by the randomization schedule, and not experiencing any other major protocol deviations prior to their week 12 visit. Safety, immunogenicity, and efficacy analyses will all be examined for the PP population. The following subjects will be excluded from the PP population:

- Subjects who do not receive 3 administrations of study product.
- Subjects who acquire confirmed ZIKV infection on or before 1 week after third administration.
- Subjects missing baseline ZIKV serostatus.
- Subjects who received a study product administration different from the randomization assignment.
- Subjects who receive the second or third administration out of the protocol-defined windows:
- Subjects who did not meet all inclusion/exclusion criteria at the time of enrollment.
- Subjects whose study group assignment is unblinded during study follow-up (Part B).
- Subjects who receive study product via incorrect route or incomplete administration.
- For efficacy analyses subjects who do not have at least one post-administration efficacy assessment (at least one visit or PCR (or other Zika) result) following product administration 3.
- *For immunogenicity analyses* subjects who do not have NAb results 4 weeks post product administration 3 (Visit 05) or at baseline.
- For immunogenicity analyses subjects with serum sample for 4 weeks post product administration 3 (Visit 05) collected outside the protocol specified window (Day 77 to Day 91).

Subjects may be censored from the Per-Protocol Analysis for any of the following:

- Receipt of any non-study inactivated vaccination within 2 weeks of any study product administration.
- Receipt of any live attenuated vaccination within 4 of any study product administration.

- Receipt of any other investigational research agent at any time during the trial.
- Receipt of any concomitant medication that may interfere with immune response, including but not limited to:
  - Any systemic immunosuppressive or cytotoxic medical blood products within 16 weeks prior to randomization.
  - Immunoglobulin within 8 weeks prior to randomization.
  - Current anti-TB prophylaxis or therapy.
- Confirmed or suspected immunosuppressive or immunodeficient condition, including HIV infection.

All exclusions from analysis populations and censoring events will be reviewed by the Protocol Statistician, Protocol Chairs, and Lead Medical Officer and others on the Protocol Safety Review Team.

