## 4.3.2. Unscheduled Collection of Samples for Suspected ZIKV Infection

At any time during the study, if a subject exhibits any sign or symptom possibly consistent with a ZIKV infection, PI or designee must attempt to diagnose the infection rapidly. PCR testing must be used to test for ZIKV infection because vaccine-induced antibodies could be detected by antibody-based diagnostic tests and even mimic the antibody profile of acute or remote ZIKV infection.

Sample collection for diagnostic testing may occur during a scheduled study visit or an unscheduled visit may be conducted. All samples sent to the PDL will be tested using the RealStar® Zika Virus RT-PCR to test for ZIKV specific RNA. Upon site request, the PDL will also run the TrioPlex Real-time RT-PCR for the differentiation of ZIKV, DENV and CHIKV RNA. The site should request TrioPlex when there is suspicion of DENV and/or CHIKV based on clinical symptoms or local epidemiology in order to differentiate from ZIKV infection.

Because diagnostic testing based on ZIKV-specific antibody tests could lead to inadvertent unblinding, study staff will remind subjects that it is preferable that no testing for ZIKV infection be done outside of the trial during study participation unless required to provide care to the subject, such as if needed while traveling. If this occurs, virologic (PCR-only) test results should be provided to the study team as available so that proper documentation of ZIKV infection can occur. In addition to laboratory testing, subjects should always be evaluated using clinical judgment, local requirements, and the current CDC or WHO definitions of ZIKV infection: https://wwwn.cdc.gov/nndss/conditions/zika-virus-disease-and-zika-virus-congenital-infection/case-definition/2016/ or http://www.who.int/csr/disease/zika/case-definition/en/respectively.

In **Part A**, diagnostic testing of suspected ZIKV infections by virus detection (e.g., PCR) may be done through the PDL or by the site's local standard testing procedures. It is recommended that serum and urine be collected for laboratory testing but there is no requirement for the type or number of samples that should be collected and tested. Note that only samples collected on one day are recorded in the database if collected, additional samples must be recorded and tracked in the subject study file.

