# 6.4. Statistical Analysis

Study accrual is defined in this protocol as being randomized to a treatment group and receiving the first administration of study product. All accrued subjects will receive at least one product administration and therefore will provide some safety data. The safety population will include all enrolled subjects, summarized according to the actual vaccination dose received.

In **Part B**, all subjects will be tested for baseline ZIKV serostatus based on samples collected at Visit 02 prior to the first product administration. Since those with prior exposure to ZIKV may respond differently to the vaccine from those naïve subjects, safety, immunogenicity and efficacy will be analyzed within each stratum defined by baseline ZIKV status in addition to overall strata combined. **Part A** of the study is to be conducted at endemic or potentially endemic sites with baseline ZIKV serostatus tested, then safety and immunogenicity analyses will be similarly run by stratum in addition to overall strata combined.

Three types of analysis cohorts are defined. The Intent-to-treat (ITT) cohort will include all accrued subjects according to group assignment. The Per Protocol (PP) cohort will include all subjects receiving all planned vaccinations within window as assigned by the randomization schedule, and not experiencing any other major protocol deviations prior to the visit of

evaluation. The Modified intent-to-treat (mITT) analyses will include all accrued subjects who remain event-free one week after all planned product administration, where event is the primary efficacy event of a positive ZIKV PCR test result.

No multiple comparison adjustment will be employed for safety, immunogenicity, or efficacy analyses. Missing data will be primarily considered as missing completely at random in safety and immunogenicity analysis provided missing data is modest (e.g. <5-10%). For completeness, we will examine the missing data completely at random assumption and perform sensitivity analyses which weaken the missing completely at random assumption if the missing data is >10% or if the missing at random assumption is questionable. For efficacy, missing at random will be assumed and methods for handling missingness, such as multiple imputation and inverse propensity weighting, will be considered.

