# 6.4.3. Analysis of Immune Responses

Immunogenicity will be analyzed for a variety of cohorts defined above, and specified in the SAP (Statistical Analysis Plan). At minimum these may include ITT, PP, and mITT cohorts. Assay results will be examined to determine if their distributions should be analyzed as normal, lognormal, nominal or categorical. It may also be appropriate to dichotomize the data into "responders" and "non-responders". Immunogenicity data will be analyzed at each time point where such data is collected. Longitudinal methods will be used to estimate the nature and extent of immune response decay over time. Immunogenicity will be assessed by group. To account for preexisting immunogenicity due to prior ZIKV exposure, immunogenicity will also be assessed according to baseline serostatus as a secondary analysis.

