#### 9. IMMUNOGENICITY EVALUATION

The principal immunogenicity endpoints are measured at Day 0 (Visit 02) and 4 weeks after the third administration (Visit 05) by NAb. We assume NAb results will follow a log-normal distribution.

The following summaries will be presented by study group and study visit separately for Part A and Part B for all subjects in each of the ITT, PP and mITT analysis populations. Summaries are presented over all subjects and stratified by baseline ZIKV serostatus.

- The number and percentage of subjects with positive NAb response, defined as a titer≥30, along with their exact 95% CIs and p-values from a Chi-squared test comparing study groups. (Table 19 through Table 24, Appendix 1)
- GMTs and their CIs, p-values from a t-test comparing log-NAb titers between study groups. (Table 25 through Table 30, Appendix 1)
- Geometric mean fold rise (GMFR) in NAb from baseline with the corresponding confidence interval and (1) p-value from a paired t-test comparing the log-NAb titers between baseline and post-administration within each treatment arm, and (2) p-value from t-test comparing log-transformed fold increases in NAb between study groups. Non-parametric tests will be considered if the normality assumption is not realized. (Table 25 through Table 30, Appendix 1)
- Boxplots of NAb titers. (Figure 15 through Figure 26, Appendix 2)
- Reverse cumulative distribution curves of NAb titers. (Figure 3 through Figure 14, Appendix 2)

Exploratory analysis of NAb for other visits will be presented in a similar fashion as data are available.

A listing of individual NAb titer levels, whether positive and the corresponding planned and actual collection dates are presented in Listing 16 - Listing 17, **Appendix 3.** For any immunogenicity reports released prior to database lock and study unblinding, a coded subject identifier will be included in listings to prevent unblinding any subject's study product assignment.

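### The per-protocol set drops ZIKV infections only up to one week after dose 3, so in the exploratory later-visit NAb summaries and decay model, titers raised by later natural infection would count as persistence.

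*Combined protocol and SAP*

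**What the plan says.** SAP 9 summarises NAb in the ITT, mITT and PP populations, overall and by baseline serostatus. A response is a titer of 30 or more. SAP 6.3 treats infection as follows.

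- ITT has no infection rule.
- mITT is "all randomized subjects who remain event-free one week after all planned product administrations".
- PP excludes "Subjects who acquire confirmed ZIKV infection on or before 1 week after third administration". Its immunogenicity-specific exclusions concern only missing NAb results and out-of-window Visit 05 sera.
- A further list opens "Subjects may be censored from the Per-Protocol Analysis for any of the following". It names other vaccines, investigational agents, interfering medication and immunodeficiency, but not ZIKV infection.

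Protocol 6.4 words the PP set as "and not experiencing any other major protocol deviations prior to the visit of" evaluation. That ties eligibility to the visit, but only for protocol deviations, and an infection is not one.

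On timing, SAP 9 states: "The principal immunogenicity endpoints are measured at Day 0 (Visit 02) and 4 weeks after the third administration (Visit 05) by NAb". It adds: "Exploratory analysis of NAb for other visits will be presented in a similar fashion as data are available". Protocol 6.4.3 says: "Longitudinal methods will be used to estimate the nature and extent of immune response decay over time". Protocol 3.3 lists durability as an exploratory objective, and Part B serum is drawn to Week 96 (Protocol Appendix III, Table C).

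**The concern.** One week after dose 3 is a sensible start for counting efficacy events. It does not serve an analysis of how long vaccine-induced antibody lasts, because every infection after about Day 63 leaves that subject's later titers in the set.

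The NAb assay would be expected to read both sources together. Protocol 1.7 builds the reporter virus particles from the structural proteins of the ZIKV H/PF2013 strain, and Protocol 2.1 says the vaccine encodes prM and E of that strain. This is an inference from the antigens. Protocol 4.3.2 makes a parallel point about a different class of test: "vaccine-induced antibodies could be detected by antibody-based diagnostic tests and even mimic the antibody profile of acute or remote ZIKV infection".

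At stake are the late comparison with placebo and the vaccine arm's own decay curve. If the vaccine works, infections are more frequent under placebo. Placebo titers then rise more, which shrinks the late contrast, while the boosted vaccinees flatten the apparent decay.

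**Working it through.** **Inputs.** VE 61% (hazard ratio 0.39), 1200 per arm, 6-month accrual and yearly placebo incidence of 0.5-4% come from Protocol 6.3.2.3 and Table 10. The text before Table 11 extends the range down to 0.25%. The cut-off is dose 3 (Day 56) plus 7 days, i.e. Day 63. Visit 05 is Day 84 and Week 96 is Day 672.

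**Reproducing the plan's figure.** With exponential infection times and mean follow-up of 2 - 0.25 = 1.75 years, expected cases at 3% per year are 1200 x (1 - exp(-0.03 x 1.75)) + 1200 x (1 - exp(-0.39 x 0.03 x 1.75)) = 61.4 + 24.3 = 85.7. Table 10 gives 86, so the infection model matches the protocol's.

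**Infected share after the cut-off.** Share = 1 - exp(-rate x t), with the rate multiplied by 0.39 in the vaccine arm.

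- Visit 05: t = 21/365.25 = 0.0575 years. At 3% per year, placebo 0.17% (2.1 of 1200) and vaccine 0.07% (0.8 of 1200). At 4% per year, 2.8 and 1.1 subjects.
- Week 96: t = 609/365.25 = 1.667 years. See the table.

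**Effect on GMT.** Rise = ratio^share - 1, where ratio is the infected/uninfected titer ratio. The documents give no such ratio, so 10 and 100 are assumed, the same in both arms. At 3% per year in placebo: 10^0.0488 = 1.119 and 100^0.0488 = 1.252.

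| Placebo incidence per year | Placebo infected by Week 96 | Vaccine infected by Week 96 | Placebo GMT rise, ratio 10 to 100 | Vaccine GMT rise, ratio 10 to 100 |
|---|---|---|---|---|
| 0.25% | 0.42% (5.0) | 0.16% (1.9) | 1.0-1.9% | 0.4-0.8% |
| 0.5% | 0.83% (10.0) | 0.32% (3.9) | 1.9-3.9% | 0.8-1.5% |
| 1% | 1.65% (19.8) | 0.65% (7.8) | 3.9-7.9% | 1.5-3.0% |
| 3% | 4.88% (58.5) | 1.93% (23.2) | 11.9-25.2% | 4.5-9.3% |
| 4% | 6.45% (77.4) | 2.57% (30.8) | 16.0-34.6% | 6.1-12.6% |

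Counts in brackets are out of 1200.

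**Between-arm shift at Week 96, 3% per year.** (0.0488 - 0.0193) x ln(ratio) = 0.07 at ratio 10 and 0.14 at ratio 100. Protocol Table 8 gives 0.11 as the detectable log-scale difference at SD 1 with 1200 per group and 80% power, so the shift is of that order.

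**Visit 05 at the extreme.** At 4% per year and ratio 100, the GMT rises 1.1% in placebo and 0.4% in vaccine, and the responder rate by at most about 0.23 and 0.09 percentage points.

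**The case against.** The case for leaving the SAP alone has real force.

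- Durability and later-visit NAb are exploratory, and SAP 2.1 says exploratory endpoint analyses are not detailed there. This stands as a limit on weight. But SAP 9 still extends its presentation to other visits, and the populations it names are the ones in SAP 6.3.
- Incidence may be low. Protocol 6.3.2.3 says it may be below 2% and plans for up to 30% baseline seropositives assumed not to become infected; SAP 10 anticipates possibly only a nominal number of cases. This stands. With 30% seropositive, the 3% per year shares fall to 0.7 x 4.88 = 3.4% and 0.7 x 1.93 = 1.4%. Dropout lowers them further.
- Filtering has its own bias. Protocol 1.7 calls NAb a correlate of protection, so vaccinees with breakthrough infection may be low responders, and dropping their titers also tilts persistence upward. This stands, but it touches about 2% of vaccinees at 3% per year and can be seen against the unfiltered ITT result.

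Three stronger readings are tempting and not supported. First, a reader might infer that the Visit 05 endpoint is compromised; the figures above show it is not. Second, a reader might infer that the trial cannot answer its durability question. Infection dates and titers are both collected, and Protocol 6.4.3 leaves room for other cohorts, so only the rule is missing. Third, a reader might take Protocol 4.3.2 as saying that the NAb assay cannot separate infection from vaccination. That section concerns diagnostic tests.

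**Conclusion.** The gap is real and of moderate weight: worth closing, but not a threat to the prespecified Week 12 result. No stated population or censoring rule removes NAb results after an infection later than one week past dose 3. The consequence lies in the exploratory late summaries and the decay model. It ranges from minor (GMT rises of at most about 4% in placebo and 1.5% in vaccine at 0.5% per year) to material (about 12-25% and 5-9% at 3% per year). If the vaccine works, the late vaccine-placebo contrast is understated and vaccine-arm persistence overstated.

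The infected shares rest on a constant hazard, VE 61% from Day 63, no dropout and everyone in the PP set. The GMT effects rest in addition on titer ratios that the documents do not supply.

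**What to change.** Keep the one-week exclusion in SAP 6.3 and add, for PP immunogenicity: *NAb results from samples collected on or after the subject's ZIKV event date as defined in SAP 10.2 (the earlier of illness onset or first positive specimen, including subclinical cases found retrospectively) are excluded.* Apply it to Visit 05, every later visit and the decay model. Leave ITT unfiltered and report it alongside.

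The cost is SAP wording and one date filter. Serum and whole blood are drawn at the same scheduled visits, stored samples are already to be PCR-tested (Protocol 1.8), and SAP 10.2 already derives the date. The downside is the loss of a few percent of late titers and a PP set that conditions on infection. That may preferentially drop low-responding breakthrough vaccinees and so slightly overstate persistence; the report should say so beside the ITT result. Infections that PCR misses would remain in the set.
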